12.0 CRITERIA FOR THERAPEUTIC RESPONSE/OUTCOME ASSESSMENT

Response is defined as improvement in diarrhea by 1 grade according to the CTCAE 5.0 scale or returns to patients baseline. Resolution of diarrhea is defined as normalization of bowel habits (grade 0). Response grading according to CTCAE 5.0 definition will be assessed at baseline and after 1 week, 2 weeks, 4 weeks and the end of study at 12 weeks. When evaluating the primary endpoint based on CTCAE 5.0, the grading will be determined by recalling the average number of stools in the previous two days. In addition, GI symptoms and diet will be assessed and at baseline and after 1 week, 2 weeks, 4 weeks and at the end of study at 12 weeks.

13.0 CRITERIA FOR REMOVAL FROM STUDY

Patients will be informed that they have the right to withdraw from the study at any time for any reason, without prejudice to their medical care.

The investigator is *required* to withdraw patients from the study for any of the following reasons:

- If at any time a patient develops unacceptable toxicity from colesevelam
- General or specific changes in the patient's condition unacceptable for further treatment in the judgment of the investigator

• If there is no resolution of diarrhea to grade 0 at 2 weeks after the dose has been increased to dose level 2

The investigator may *consider* withdrawing patients from the study for any of the following reasons:

- Side effects from colesevelam
- If there is protocol violation
- Non-compliance
- Administrative reasons
- Failure to return for follow-up

14.0 BIOSTATISTICS

Primary Objective:

This is a phase 2, open label, single arm study to evaluate the efficacy of colesevelam to improve lenalidomide-associated diarrhea in patients with multiple myeloma treated with lenalidomide maintenance. There is limited data on the resolution of lenalidomide-associated diarrhea in this patient population. However, if 10% or less of patients have an improvement by 1 grade or returns to patients baseline when receiving colesevelam within the first 4 weeks or starting colesevelam, the intervention will not be considered promising. If 30% of patients or more have a reduction to grade 0 diarrhea or returns to patient's baseline, the intervention will be considered promising and worthy of further investigation. The intervention will be considered a success if at any point the patient had an improvement to grade 0 diarrhea or returns to patients baseline within the first 4 weeks or starting colesevelam. Based on these rates, a Simon two-stage minimax design will be employed. In the first stage of the study, 16 patients will accrue. If one or fewer patients have a reduction in diarrhea severity, the study will stop due to a lack of efficacy; otherwise, an additional 9 patients will accrue. If at the end of study more than 4 out of the 25 total patients have a reduction in diarrhea to grade 0 or to patient's baseline by the week 4 evaluation, the study will be considered promising. The type I and type II errors are both set at 0.10.

Patients who are removed from study before the 1-week evaluation for reasons unrelated to worsening of diarrhea, or drug-related toxicity will be considered nonevaluable and will be replaced for the primary analysis. Patients removed from study for worsening of diarrhea, a lack of improvement in diarrhea, or drug-related toxicity within the first 4 weeks of the study will be considered treatment failures.

Secondary Objectives:

- GI symptoms will be evaluated throughout the study using the PRO-CTCAE questionnaire for GI symptoms. This questionnaire will be evaluated at baseline and weeks 1, 2, 4, and 12. Individual components of the PRO-CTCAE GI will be summarized longitudinally for each patient.
- Patient's dietary intake will be recorded with the aim of assessing whether patients have changed their diet due to the diarrhea and whether patients go back to their normal diet if

the diarrhea responds to colesevelam. The proportion of patients who have had a change in their diet due to diarrhea, and the proportion who had a diet change due to either lenalidomide or colesevelam will be reported

- Patient diarrhea will be further summarized during the study period using the Bristol Stool Form Scale. The scale has seven types of stool consistency. The proportion of patients with improvements in stool consistency from baseline to weeks 1, 2, 4, and 12 will be calculated along with a 95% exact confidence interval.
- The proportion of patients with sustained response by week 12 (end of study) will be calculated with a 95% exact confidence interval. This is calculated as the proportion of patients who have grade 0 diarrhea at week 12 among patients who achieved grade 0 diarrhea by the week 4 assessment.

Correlative studies

Lenalidomide pharmacokinetics while on colesevelam will be described in up to 15 patients treated on this study; the changes from baseline will be reported.

Stool samples will be analyzed for changes in gut microbiota that take place before and after 12 week of colesevelam treatment. Changes in alpha diversity will be summarized using average change in the Inverse Simpson index. Microbial ecology and metagenomic analysis will be performed to describe changes in gut microbiota throughout the study.

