1.0 PROTOCOL SUMMARY AND/OR SCHEMA

Title

Colesevelam for lenalidomide-associated diarrhea

Primary Objective

The primary objective is to evaluate the ability of colesevelam to improve lenalidomideassociated diarrhea in patients with multiple myeloma treated with lenalidomide maintenance.

Patient population

Patients with multiple myeloma, age 18 years or older, treated with maintenance lenalidomide. Patients who experience grade 1 or worse diarrhea on lenalidomide will be treated with colesevelam.

Study design

This is a single arm, phase II trial of colesevelam for lenalidomide-associated diarrhea. Up to 40% of myeloma patients on lenalidomide maintenance experience some degree of diarrhea. There is currently no established treatment standard for patients who develop diarrhea during lenalidomide and available anti-diarrheal (i.e. loperamide, opioids) may not give optimal symptom relief. In this trial we will assess whether colesevelam, a bile acid sequestrant, can improve diarrhea associated with lenalidomide maintenance therapy in patients with grade 1 or more diarrhea. The target will be that 30% of patients with lenalidomide-associated diarrhea will have an improvement by at least 1 grade or returns to patients baseline when receiving colesevelam. A total of 25 patients will accrue on the study in a Simon's two-stage minimax design. Patients will initially be started on 1250 mg (2 x 625 mg tablets) and the dose can be increased to maximum of 6 tablets per day based on efficacy and tolerability. Treatment will be continued until drug-related toxicity, worsening of diarrhea, or diarrhea that remains grade 1 or higher at week 2. Each patient will be followed for 12 weeks after colesevelam initiation.

Secondary objectives in the study include assessment of gastrointestinal (GI) symptoms the Patient Reported Outcomes within the Common Terminology Criteria for Adverse Events (PRO-CTCAE), as well as assessment of diet using a dietary questionnaire.

Lenalidomide pharmacokinetics will be assessed in up to 15 patients to assess possible drug interactions between lenalidomide and colesevelam. In these patients, a blood sample will be drawn pre- and 2 hours post the first colesevelam dose (day 1), as well as pre- and 2 hours post colesevelam on day 8 after initiation of colesevelam. Research stool samples will be collected at baseline and after 12 weeks of treatment for microbiota and bile acid studies.

Treatment Plan

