2.0 OBJECTIVES AND SCIENTIFIC AIMS

Primary objective

To evaluate the ability of colesevelam to improve lenalidomide-associated diarrhea in patients with multiple myeloma treated with lenalidomide maintenance. Diarrhea will be evaluated using Common Terminology Criteria for Adverse Events (CTCAE) grading. The primary end-point is improvement of diarrhea by at least 1 grade or returns to patients baseline when receiving colesevelam according to CTCAE 5.0 scale by 4 weeks of treatment with colesevelam.

Secondary objective

- To assess GI symptoms using the Patient Reported Outcomes within the Common Terminology Criteria for Adverse Events (PRO-CTCAE)
- To assess diet before and while on treatment with colesevelam.
- To further describe diarrhea during the study period using the Bristol Stool Form Scale.3
- Describe duration of response by week 12 (end of study)

Correlative studies

- To assess lenalidomide pharmacokinetics while on colesevelam
- Collection of research stool samples for GI microbiota and bile acid assessment

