4.0 OVERVIEW OF STUDY DESIGN/INTERVENTION

4.1 Design

This is a single institution, single arm, open label phase II trial to evaluate the efficacy of colesevelam for myeloma patients on lenalidomide maintenance who experience grade 1 or more diarrhea. Patients will be given colesevelam at a starting dose of 2 tablets (2 x 625 mg) which can be increased to up to 6 tablets per day depending on efficacy and tolerability, see dose adjustment schedule section 9.2, page 16. Patients can continue on the study until unacceptable toxicity, diarrhea that remains grade 1 or higher at week 4, worsening of diarrhea at any point, or end of study (12 weeks), whichever comes first. Each patient will be followed for a total 12 weeks.

The primary endpoint of this study is improvement of diarrhea. Response is defined as improvement by at least 1 grade according to CTCAE version 5.0 (see page 15) or returns to patients baseline when receiving colesevelam. A total of 25 patients will accrue on the study in a Simon's two-stage minimax design. In the first stage of the study, 16 patients will accrue. If 1 or fewer patients have a reduction in diarrhea severity, the study will stop due to a lack of efficacy; otherwise, an additional 9 patients will accrue. We estimate that the accrual to the study will be approximately two patients per month. The study is expected to be completed in approximately two years.

A diarrhea diary will be filled out by patients to capture frequency and consistency of bowel movements. GI symptoms will be assessed using the GI oriented PRO-CTCAE questions. Diet will be recorded at several time points to assess changes in dietary intake prior to and while on colesevelam. Stool consistency will be assessed using the Bristol Stool Form Scale. Correlative studies include pharmacokinetic (PK) evaluation of lenalidomide as well as collection of stool for studies of the GI microbiome.

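### The final decision rule counts grade 0 or return to baseline, while the declared primary endpoint also counts any 1-grade improvement, so the same 25 patients can pass one and fail the other

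*Combined protocol and SAP*

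**What the plan says.** The endpoint sections agree with each other. Section 2.0 states: "The primary end-point is improvement of diarrhea by at least 1 grade or returns to patients baseline when receiving colesevelam". Section 4.1 says "Response is defined as improvement by at least 1 grade according to CTCAE version 5.0" and adds return to baseline as an alternative. Section 12.0 repeats this and defines grade 0 separately, as resolution. Section 1.0 sets the target on the same event: "30% of patients with lenalidomide-associated diarrhea will have an improvement by at least 1 grade or returns to patients baseline".

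Section 14.0 uses three wordings:

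- **Null (10%)**, on the declared endpoint: "if 10% or less of patients have an improvement by 1 grade or returns to patients baseline when receiving colesevelam".
- **Alternative (30%)**, on grade 0 or baseline: "If 30% of patients or more have a reduction to grade 0 diarrhea or returns to patient's baseline, the intervention will be considered promising".
- **Patient-level success**, on grade 0 or baseline: "considered a success if at any point the patient had an improvement to grade 0 diarrhea or returns to patients baseline".
- **Stage 1 stop**, on any reduction in severity: "If one or fewer patients have a reduction in diarrhea severity, the study will stop due to a lack of efficacy".
- **Final rule**, on grade 0 or baseline: "more than 4 out of the 25 total patients have a reduction in diarrhea to grade 0 or to patient's baseline".

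The sustained-response proportion in Section 14.0 counts grade 0 only. Nothing in the document reconciles these wordings.

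**The concern.** Return to baseline belongs to both definitions, so the conflict is between a 1-grade improvement and grade 0. For a patient entering at grade 1 the two are the same. Section 6.1 admits grade 1 or more, so patients can enter at grade 2 or worse. One of these who improves by a grade without reaching grade 0 or baseline counts as a responder in Sections 2.0, 4.1 and 12.0 and, on the natural reading, at stage 1, but not in the final rule.

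The cut-off is 4, so one or two such patients can decide the result. In an open-label single-arm trial with two definitions in force, the choice could be made after the data are seen. If the final rule is applied as written, the trial also loses power for its declared endpoint at its stated target.

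**Working it through.** **Inputs.** From Section 14.0: stage 1 n = 16, stop if 1 or fewer; total n = 25, promising if more than 4; rates 10% and 30%; both errors set at 0.10. The documents do not give the share of 1-grade responders who stop short of grade 0 or baseline. Call it f and take an assumed range of 0 to 50%.

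**Step 1: the plan's design with one endpoint.** Let X be the stage 1 responders, Bin(16, p), and Y the stage 2 responders, Bin(9, p).

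P(promising) = Σ over x ≥ 2 of P(X = x) × P(Y ≥ 5 − x)

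| x | p = 0.10 | p = 0.30 |
|---|---|---|
| 2 | 0.2745 × 0.0530 = 0.0145 | 0.0732 × 0.5372 = 0.0393 |
| 3 | 0.1423 × 0.2252 = 0.0321 | 0.1465 × 0.8040 = 0.1178 |
| 4 | 0.0514 × 0.6126 = 0.0315 | 0.2040 × 0.9596 = 0.1958 |
| 5 or more | 0.0170 | 0.5501 |
| Total | **0.0951** | **0.9030** |

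An exhaustive search confirms 1/16, 4/25 as the minimax design for these rates. The arithmetic is correct when every element refers to one event.

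**Step 2: a data set with opposite conclusions.** Four of 25 patients reach grade 0 or baseline, three others go from grade 2 to grade 1, and at least two of the seven are in stage 1. The declared endpoint gives 4 + 3 = 7, which exceeds 4: promising. The final rule gives 4, which does not exceed 4: not promising.

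**Step 3: the rule as written.** Let q be the rate on the declared endpoint and s = q(1 − f) the rate of grade 0 or baseline. Read the stage 1 wording as the declared endpoint. Each stage 1 patient is then strict (s), partial (q − s) or neither (1 − q). With x strict and y partial patients:

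P(promising) = Σ over x + y ≥ 2 of [16! / (x! y! (16 − x − y)!)] s^x (q − s)^y (1 − q)^(16 − x − y) × P(Bin(9, s) ≥ 5 − x)

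The definitions are nested, so every pass on the rule as written is also a pass on the declared endpoint. The chance of opposite conclusions on the same patients is therefore 0.9030 minus P(promising). At the Section 1.0 target, q = 0.30:

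| f | s = 0.30 × (1 − f) | P(promising), rule as written | P(opposite conclusions) |
|---|---|---|---|
| 0% | 0.30 | 0.903 | 0 |
| 10% | 0.27 | 0.841 | 0.062 |
| 15% | 0.255 | 0.799 | 0.105 |
| 20% | 0.24 | 0.749 | 0.154 |
| 30% | 0.21 | 0.625 | 0.278 |
| 40% | 0.18 | 0.476 | 0.427 |
| 50% | 0.15 | 0.317 | 0.586 |

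Reading stage 1 as grade 0 or baseline too changes little: 0.837, 0.742, 0.617, 0.468 and 0.310 at f = 10, 20, 30, 40 and 50%.

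**Step 4: link to entry grade.** f = (share of responders who entered at grade 2 or worse) × (share of those who stop short). If half stop short, entry shares of 20%, 40% and 60% give f = 10%, 20% and 30%, hence power 0.84, 0.75 and 0.63. If all responders entered at grade 1, f = 0 and power stays at 0.903.

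**Step 5: error rates under Section 14.0's own hypotheses.** With q = 0.10 and any s up to 0.10, the maximum chance of a promising result is 0.0951. With s = 0.10 and any q, the maximum is 0.0980. With s = 0.30 and any q, power is at least 0.9030.

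**The case against.** The size of the loss is assumed. The documents give neither the entry-grade mix nor the shortfall. Section 3.0 puts grade 3 or 4 diarrhea at about 2–3% of patients against 25–40% for any grade, so severe entrants are probably few. If nearly everyone enters at grade 1, the conflict has almost no numerical effect. This stands, and the 50% row should not be read as the expected case. The only related data are in the case series in Section 3.0: of 10 patients given colesevelam, 5 normalised and 5 improved. Grades were not reported, so this cannot fix f, but it does not support assuming that f is negligible.

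The loss also depends on holding the declared-endpoint rate at 30%. With f = 50% and rates of 40%, 50% and 60%, the rule as written passes with probability 0.58, 0.79 and 0.91. That is correct, but 30% is the plan's own target and the point at which its power is stated.

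The error is conservative: type I error holds, and the sample size and cut-offs survive. That also stands. The case for a correction rests first on the ambiguous decision rule and only second on the power table.

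Finally, the documents do not settle which event was intended. Grade 0 also appears in the sustained-response measure and in some removal rules, so either choice is open to the sponsor.

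**Conclusion.** The concern holds and must be fixed before analysis. The primary decision rule does not test the declared primary endpoint, and Section 14.0 places its null and its alternative on different events. One data set can give opposite conclusions, always in the same direction: promising on the declared endpoint and not promising under the final rule.

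At the 30% target, power falls from 0.903 to below 0.80 once about 15% of responders stop short of grade 0 or baseline, and to 0.63 at 30%. These figures rest on an assumed shortfall and on reading the stage 1 wording as the declared endpoint. The contradiction itself rests on no assumption. Type I error stays within 0.10, and the sample-size arithmetic is right.

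**What to change.** State one response definition and use it for the null, the alternative, the stage 1 count, patient-level success, the final count and sustained response. There are two options:

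1. Keep the definition in Sections 2.0, 4.1 and 12.0 (at least 1-grade improvement or return to baseline), rewrite Section 14.0 to match, and report grade 0 resolution as a secondary proportion with an exact confidence interval. This is the default, because it is the declared endpoint and carries the 30% target in Section 1.0.
2. Make grade 0 or return to baseline primary, and change Sections 1.0, 2.0, 4.1 and 12.0 and the stage 1 wording to match.

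Under either option, confirm that 10% and 30% are the intended rates for the chosen event. If so, 16/25 with cut-offs 1 and 4 stays; if not, recalculate the design.

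The removal rules in Sections 4.1, 4.2, 9.2, 10.10 (Table 4, footnote b) and 13.0 use different grade criteria and times. They contradict one another and must be reconciled, because they decide whether a partial responder is still on study at week 4. Which rule is right is a clinical matter outside this point.

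The cost is a wording amendment. Data collection does not change, and neither does the sample size if the rates are confirmed.

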9.3 Concomitant medications

No other antidiarrheals will be allowed while on study treatment with colesevelam to evaluate efficacy accurately. If the diarrhea is worsening while on colesevelam, the patient will be

taken off study and can then start other anti-diarrheal medications. Similarly, if there is no sign of improvement after start of colesevelam despite dose escalation by 2 weeks, the patient will be taken off study and is allowed to start other anti-diarrheal medications.

Orally administered drugs that have not been tested for interaction with colesevelam, especially those with a narrow therapeutic index, should be administered at least 4 hours prior to colesevelam. Therefore, lenalidomide should be spaced out from colesevelam by 4 hours at least. In addition, the physician should monitor drug levels of the co-administered drugs. Medications with known drug interactions are listed under section 5.0 page 11.

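### Section 14.0 makes a patient who leaves before the 1-week evaluation for lack of improvement both replaceable and a treatment failure, and the design has almost no type I error to spare

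*Combined protocol and SAP*

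**What the plan says.** Section 14.0 gives a replacement rule and a failure rule in consecutive sentences.

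- Replacement rule: "Patients who are removed from study before the 1-week evaluation for reasons unrelated to worsening of diarrhea, or drug-related toxicity will be considered nonevaluable". These patients are then replaced for the primary analysis. The only exceptions are worsening and drug-related toxicity.
- Failure rule: patients removed for worsening, "a lack of improvement in diarrhea, or drug-related toxicity within the first 4 weeks of the study will be considered treatment failures". This list has three reasons, and its 4-week period includes the first week.

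Section 13.0 lets patients withdraw at any time for any reason. It also lists grounds on which the investigator may consider withdrawing a patient, among them protocol violation, non-compliance and "Failure to return for follow-up". Section 9.3 adds: "No other antidiarrheals will be allowed while on study treatment with colesevelam to evaluate efficacy accurately".

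The 1-week evaluation has a window of 2 days either side in Sections 4.2 and 10.4. Table 4 allows the Day 8 visit 7 days either side.

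**The concern.** Lack of improvement is in the failure rule but not among the exceptions to the replacement rule. A patient who gives up in the first days because the drug is not working is nonevaluable and replaced under one sentence, and a treatment failure under the next. Neither sentence is said to take precedence.

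The choice matters because the Simon boundaries assume a fixed 16 and 25 patients. If a non-responder is taken out and a new patient put in, the trial gets another chance at a response while the boundaries stay where they are. In an open-label, single-arm study, the recorded reason for leaving would then decide whether the patient counts.

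There is also a gap. A patient who passes the 1-week evaluation and leaves before week 4 through non-compliance, protocol violation, failure to return or voluntary withdrawal fits neither rule, so the plan does not say how that patient enters the 16 or the 25.

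**Working it through.** **Inputs.** All are from Section 14.0. The null rate is 0.10 ("if 10% or less of patients have an improvement by 1 grade or returns to patients baseline") and the target rate 0.30 ("If 30% of patients or more have a reduction to grade 0 diarrhea or returns to patient's baseline"). Those two sentences describe success differently; that is a separate matter, and here success is one yes/no outcome with rate p. The plan states that "a Simon two-stage minimax design will be employed": stop at 1 or fewer of 16, and call the result promising at 5 or more of 25. "The type I and type II errors are both set at 0.10". The documents give no replacement rate, so every share below is an assumption.

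**1. The plan's own figure.** P(promising) = sum over x = 2 to 16 of Bin(x; 16, p) × P(Y ≥ 5 − x), with Y ~ Bin(9, p).

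- p = 0.10: 0.0951, with probability 0.515 of stopping after stage 1.
- p = 0.30: 0.9030.

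A search over two-stage designs returns this same design as the minimax, so the design is correctly stated. The room left under the limit is 0.10 − 0.0951 = 0.0049.

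**2. Exactly one non-responder replaced.** The evaluable patients then carry all the responses from one extra enrolled patient, with the bounds unchanged.

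- Replaced in stage 1 (17 enrolled, then 9): type I error 0.109.
- Replaced in stage 2 (16 enrolled, then 10): 0.107.
- Two replaced: 0.124 or 0.120.

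**3. A share f of enrolled patients replaced, all non-responders.** The response rate among evaluable patients becomes 0.10/(1 − f), which goes into the formula in step 1.

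| f (assumed) | 0.10/(1 − f) | Type I error |
|---|---|---|
| 0 | 0.1000 | 0.0951 |
| 1% | 0.1010 | 0.0983 |
| 2% | 0.1020 | 0.1016 |
| 5% | 0.1053 | 0.1124 |
| 10% | 0.1111 | 0.1334 |

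The limit is reached at an evaluable rate of 0.10154, which is f = 1 − 0.10/0.10154 = 1.5%. One patient replaced out of 26 enrolled is 1/26 = 3.8%; this formula then gives 0.108, in line with step 2. If replacement is unrelated to outcome, the evaluable rate stays at 0.10 and the error at 0.0951.

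**4. Exits between week 1 and week 4 for other reasons.** The text does not allow these patients to be replaced. Kept in the 25 as non-responders, they leave type I error at 0.0951 or below. If one is dropped from stage 2 without replacement and regardless of outcome, with the bounds kept (16, then 8), the error falls to 0.083. If the dropped patient is a sure non-responder, the count of responses does not change, so the decision does not either. What changes is the reported proportion: 5/25 = 20.0% against 5/24 = 20.8%.

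**5. Visit windows.** Under Sections 4.2 and 10.4 the 1-week evaluation falls at most 7 + 2 = 9 days after the start. Under Table 4 the Day 8 visit may fall as late as Day 15, and the Day 15 visit as early as Day 8. On Table 4's windows, a patient judged unimproved at 2 weeks could still be ahead of the 1-week evaluation, and so inside the replacement period.

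**The case against.** The strongest reply is that the collision has a narrow route. No stated criterion removes a patient for lack of improvement before week 2; other passages put it later still. The removal rule specific to the first week is worsening, which the replacement rule already excepts, as it does toxicity. A sensible reader could also treat the failure rule as the more specific and let it prevail. The point about frequency stands: the case needs a voluntary withdrawal or the Table 4 window. The point about precedence does not settle the matter, because the plan leaves it to whoever classifies the patient.

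Three stronger readings are tempting, and the documents do not support them.

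- A reader might infer that the week 1 to week 4 gap also raises type I error. Replacement is permitted only before the 1-week evaluation, so under the text it does not (step 4).
- A reader might infer large inflation by supposing that 15% or 20% of patients are replaced non-responders, which would give 0.159 or 0.190. No such rate is in the documents. A 20% share means 25/0.80 − 25 = 6.25 replaced patients, all non-responders and all leaving before the 1-week evaluation for a reason other than worsening or toxicity.
- A reader might infer that anyone who takes a barred antidiarrheal must be removed as a violation and so escapes the failure rule. Sections 9.2 and 13.0 say only that the investigator may consider withdrawal on that ground. Section 9.3 takes patients with worsening, or with no improvement by 2 weeks, off study before another agent is started, and both groups are failures under Section 14.0.

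**Conclusion.** The contradiction is real and sits in the rule that defines the primary count. Its likely size is small: about 0.107 to 0.109 if one non-responder is replaced, against 0.0951 as designed and a limit of 0.10. Larger figures depend on assumed shares, and all of them require the replaced patients to be non-responders. The point deserves correction because a single such replacement exceeds the stated limit. The week 1 to week 4 gap is a lesser, separate defect: it leaves the denominator undefined without itself raising the false-positive risk.

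**What to change.** Amend Section 14.0 in two places and reconcile a third.

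1. Add lack of improvement, including leaving in order to use another antidiarrheal, to the exceptions in the replacement rule. Such patients are then failures and are not replaced.
2. State that every patient who reaches the 1-week evaluation stays in the 16 and the 25, and counts as a non-responder if no success is documented by week 4, whatever the reason for leaving.
3. Reconcile the 1-week visit window between Sections 4.2 and 10.4 and Table 4, so that the end of the replacement period is fixed.

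No new data or extra patients are needed. The observed rate may be slightly lower, and power has little room. If 5% of would-be responders leave before a success is documented, the target rate becomes 0.30 × 0.95 = 0.285 and power falls from 0.903 to 0.873. At 10% it is 0.30 × 0.90 = 0.27, with power 0.837. Both are below the planned 0.90, and the sponsor should accept that openly when adopting the rule.

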There is increasing data on the use of colesevelam in patients with diarrhea due to bile acid malabsorption in the setting of Crohn's disease and irritable bowel syndrome. 11,12 There are also anecdotal reports that suggest that patients with lenalidomide-associated diarrhea might benefit from dietary modifications and/or colesevelam. 10 In the above mentioned case series of 12 patients with GI symptoms (including diarrhea, urgency, fecal incontinence, and abdominal cramps) after starting lenalidomide; all patients were treated with low-fat diet and/or colesevelam. Two patients had improved symptoms on low-fat diet only. The remaining 10 patients were treated with colesevelam (+/- low-fat diet) in doses up to 6 tablets of 625 mg per day, split into doses with food and > 4 hours before or after lenalidomide administration. Of these 10 patients, 5 had normalization of bowel habits; the other 5 had improved symptoms with reductions in stool frequency and/or improvement in stool consistency.¹⁰ In the case series of 12 patients, however, there is no information on severity (i.e. grade) of diarrhea, neither at baseline nor after intervention. The authors conclude that bile acid malabsorption is a major cause of lenalidomide-associated diarrhea and can be improved by using bile acid sequestrants such as colesevelam. 10 Confirmatory clinical trials are warranted to confirm the benefit of a bile acid sequestrant in lenalidomide-associated diarrhea.

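### The Section 14 'sustained response' figure measures sustained grade 0 (resolution), so for patients entering at grade 2 or higher it does not describe duration of response as the protocol defines it

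*Combined protocol and SAP*

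**What the plan says.** The last secondary objective in Section 2.0 reads "Describe duration of response by week 12 (end of study". Section 14.0 serves it with one statistic: "The proportion of patients with sustained response by week 12 (end of study) will be calculated with a 95% exact confidence interval". The next sentence there fixes the calculation as the proportion of "patients who have grade 0 diarrhea at week 12 among patients who achieved grade 0 diarrhea by the week 4 assessment".

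Response is defined elsewhere in wider terms:

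- Section 2.0: "The primary end-point is improvement of diarrhea by at least 1 grade or returns to patients baseline when receiving colesevelam", by 4 weeks.
- Section 4.1: "Response is defined as improvement by at least 1 grade according to CTCAE version 5.0", or a return to the patient's baseline.
- Section 12.0: "Response is defined as improvement in diarrhea by 1 grade according to the CTCAE 5.0 scale or returns to patients baseline".

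Section 12.0 then gives grade 0 a name of its own: "Resolution of diarrhea is defined as normalization of bowel habits (grade 0". Section 14.0 is not uniform on the primary endpoint. It ties the unpromising rate of 10% to a 1-grade improvement or return to baseline, but ties the promising rate of 30%, the success rule and the final count to grade 0 or return to baseline.

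**The concern.** In the protocol's own vocabulary, the statistic labelled sustained response is sustained resolution. A reader will set the week 12 figure beside the primary response rate and take it as the share of responders who kept their response. If response means what Sections 2.0, 4.1 and 12.0 say, two groups are handled differently from that reading:

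- Responders who improve by a grade or more without reaching grade 0 appear in neither numerator nor denominator.
- Patients who reach grade 0 and slip back part of the way, while still a grade better than at entry, count as having lost response.

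The objective would then have no analysis that answers it for partial responders.

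**Working it through.** **The plan's own figures.** Section 14.0 states no expected value for the sustained-response proportion. Its Simon design does reproduce. With 10% against 30%, stopping at 1 or fewer of 16 and requiring more than 4 of 25, the exact type I error is 0.0951 and the power 0.9030. A minimax search returns the same design. Nothing below alters it.

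**Step 1: apply both rules to the same records.** Inputs are entry at grade 1 or more (Section 6.1), the Section 14.0 durability rule, and the response definition read as at least 1 grade better than at entry (Sections 2.0 and 4.1).

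| Entry grade | Best grade by week 4 | Week 12 grade | In Section 14.0 denominator | Sustained under Section 14.0 | Still a response at week 12 |
|---|---|---|---|---|---|
| 1 | 0 | 0 | yes | yes | yes |
| 1 | 0 | 1 | yes | no | no |
| 2 | 0 | 1 | yes | no | **yes** |
| 2 | 1 | 1 | **no** | not counted | **yes** |
| 3 | 0 | 1 or 2 | yes | no | **yes** |
| 3 | 1 or 2 | 1 or 2 | **no** | not counted | **yes** |

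At entry grade 1 a 1-grade improvement is grade 0, so the rules agree. From entry grade 2 upward they part in both ways described.

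**Step 2: illustrate the size.** These counts are assumptions.

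- Responders: 30% of 25 is 7.5, taken as 8.
- Split: 4 reach grade 0 and 4 improve without reaching it. The even split is borrowed from the case series in Section 3.0: "Of these 10 patients, 5 had normalization of bowel habits; the other 5 had improved symptoms". That series carried no grades, so it only suggests a scenario.
- Of the 4 at grade 0 by week 4, 3 are at grade 0 at week 12.

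As written: 3/4 = 75%, Clopper-Pearson 95% CI 19.4% to 99.4%, a width of 80 points.

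Over all responders: (3 + j + k)/8. Here k = 0 to 4 is the number of partial responders still responding. The term j is 1 if the fourth grade-0 patient entered at grade 2 or higher and is still at least a grade better than at entry, and 0 otherwise.

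- Lowest: (3 + 0 + 0)/8 = 37.5%, which is 37.5 points below the plan's figure.
- Highest: (3 + 1 + 4)/8 = 100%, which is 25 points above it.

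**Step 3: a second scenario, also assumed.** Of 8 responders, 5 reach grade 0. At week 12, 3 of the 5 are at grade 0, 1 who entered at grade 2 is at grade 1, and 1 has lost response. Of the 3 partial responders, 2 are still improved. The plan gives 3/5 = 60% (exact CI 14.7% to 94.7%). The response definition at both ends gives (3 + 1 + 2)/8 = 6/8 = 75% (34.9% to 96.8%).

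**Step 4: the null case.** If every patient enters at grade 1, the difference through the 1-grade route is zero.

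**The case against.** Four arguments narrow the point.

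**The formula is explicit.** Section 14.0 states what it counts, so this is a clearly stated quantity under an imprecise label. That stands. Calling the estimate biased would go too far: it is a valid estimate of sustained resolution. It does not answer the stated objective.

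**Return to baseline.** A reader might infer that patients counted as successes by returning to baseline are routinely dropped. The documents do not support that. Table 2 grades stool count as an increase over baseline, so a patient back at baseline would ordinarily be grade 0. The protocol lists the two as alternatives and never equates them, so a small gap remains.

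**The primary definition.** A reader might also infer that the mismatch survives however the primary endpoint is settled. That is too strong. If grade 0 or return to baseline governs, the durability rule nearly matches it. If the 1-grade definition governs, as Sections 2.0, 4.1 and 12.0 say, the mismatch remains in full.

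**Stopping passages.** Partial responders may not reach week 12. Sections 1.0, 4.2 and 9.2 stop treatment for grade 1 or higher at week 2. Section 4.1 places that limit at week 4. Section 13.0 requires withdrawal without grade 0 two weeks after dose level 2. Sections 9.1 and 9.3 instead refer to diarrhea that has not improved by 2 weeks, and note b to Table 4 removes only patients without a 1-grade improvement or return to baseline by the end of Cycle 1. A grade 0 durability rule fits the first group and not the second. These passages contradict one another. They determine how many partial responders have week 12 data, but none of them brings Section 14.0 into line with the response definition.

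**Conclusion.** The point holds for patients entering at grade 2 or higher. The rule omits responders who never reach grade 0 and scores some continuing responders as lost. The discrepancy is nil at entry grade 1 through the 1-grade route and minor through return to baseline.

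The size cannot be fixed from the documents, because they give no entry-grade mix. In the first illustration the share of all responders still responding lies anywhere from 37.5 points below to 25 points above the reported 75%, so the direction is unknown too. That range rests on the assumed 8 responders and even split. Section 1.0 attaches the 30% target to a 1-grade improvement, but Section 14.0 attaches it to grade 0 or baseline. On the latter reading, about 8 would already be close to the grade 0 denominator.

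It would be wrong to conclude that the trial's decision is affected. This is a descriptive secondary proportion with no test or threshold, and the Simon rule and sample size are unchanged. It should be corrected as a matter of consistency and interpretation.

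**What to change.** Replace the calculation in Section 14.0 with wording to this effect: *the proportion of patients who at week 12 still meet the response definition used for the primary endpoint, among all patients counted as responders in the primary analysis, with a 95% exact confidence interval. Responders removed before week 12 remain in the denominator as not sustained, and their number is reported.* Keep the present proportion as an additional result labelled sustained resolution. Relabelling alone would correct the name but leave the Section 2.0 objective without a matching analysis.

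Two sets of passages must be reconciled at the same time: the primary response definition (Sections 2.0, 4.1 and 12.0 against 14.0), and the stopping and removal passages (Sections 1.0, 4.1, 4.2, 9.1, 9.2, 9.3, 13.0 and note b to Table 4). Which clinical rule should prevail is for the investigators. Because the new wording refers to the primary definition, it will follow whichever definition is chosen.

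The cost is a short change to the text and one extra proportion. Section 10.4 already schedules CTCAE grading at baseline and weeks 1, 2, 4 and 12, so no further patients or assessments are needed. One drawback is that counting early removals as not sustained partly reflects the removal rules and not a return of diarrhea, which is why their number should be shown.
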